**A Double-Blind Randomized Controlled Trial on the Efficacy of Hydrocolloid
Dressing vs. Topical Antibiotic on Wound Healing of Post-Punch Biopsy
Wounds Among Patients in a Tertiary Hospital in Manila**

[name] [name]

[name], FPDS

University of Santo Tomas Hospital, [name]

Department of Dermatology

TITLE: A Double-Blind Randomized Controlled Trial on the Efficacy of Hydrocolloid Dressing vs. Topical Antibiotic on Wound Healing of Post-Punch Biopsy Wounds Among Patients in a Tertiary Hospital in Manila

[name], [name]

Resident, Department of Dermatology; Consultant, Department of Dermatology

PROJECT SUMMARY

Rationale:

Objectives: The main objective of this study is to determine the efficacy of using hydrocolloid dressing on wound healing of post-punch biopsy wounds vs topical antibiotic. Specifically, it aims to measure the following parameters: the presence or absence of infection, the clinical estimate of reepithelialization, the clinical estimate of wound closure, scar formation, pigmentation of scar, and the cosmetic appearance of the wound.

Methodology and Population: The study is a double-blind randomized controlled trial which will be conducted at the Dermatology outpatient department and the private clinics of dermatology consultants of the University of Santo Tomas Hospital. Patients who will be included are those who are 18 to 64 years of age with clean cutaneous lesions. Excluded from this study are those who have infected wounds, those who have conditions with poor tendency to heal including diabetes mellitus, peripheral vascular disease, history of keloid formation, those currently receiving anticoagulation therapy or systemic corticosteroids, and those known to have hypersensitivity to topical antibiotics.

Time Frame: 6 months

Expected Outcomes: The primary outcome measure is the proportion of patients who achieved better overall healing when treated with hydrocolloid dressing.

GENERAL INFORMATION**PROTOCOL TITLE:**

**A DOUBLE-BLIND RANDOMIZED CONTROLLED TRIAL ON THE
EFFICACY OF HYDROCOLLOID DRESSING VS. TOPICAL ANTIBIOTIC ON
WOUND HEALING OF POST-PUNCH BIOPSY WOUNDS AMONG
PATIENTS IN A TERTIARY HOSPITAL IN MANILA**

NAME AND ADDRESS OF SPONSOR/FUNDER:

NOT APPLICABLE

NAME AND ADDRESS OF AUTHORS:

[name] [name]

[name], FPDS

University of Santo Tomas Hospital, [name]

BACKGROUND

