Specifically, this study aims to compare the efficacy of hydrocolloid dressing after 5 days post-punch biopsy by measuring the following parameters: absence or presence of infection, clinical estimate of reepithelialization, clinical estimate of wound closure, scar formation, pigmentation of scar and cosmetic appearance of wound.

METHODOLOGY

A. Study Design

This is a double blind randomized controlled trial that will be conducted at the outpatient department of the University of Santo Tomas Hospital Department of Dermatology. Permission letters from the Head of Ambulatory Care Services (ACS), the Data Privacy Officer (DPO), and the Medical Director of UST Hospital will be obtained prior to the implementation of this study. Permission letters from the USTH Dermatology consultants for their private patients will be obtained prior to the implementation of this study.

[figure not shown]

Figure 1. Schematic diagram of the study design

B. Patient Selection, Recruitment and Withdrawal

Adult patients 18 to 64 years old with clean cutaneous lesions who will undergo skin punch biopsy using a 3-mm disposable biopsy puncher shall be included in the study.

Patients will be recruited from the UST Hospital outpatient department and from the private clinics of the UST Hospital Dermatology consultants. Patients who have infected wounds, patients who have conditions with poor tendency to heal including diabetes mellitus, peripheral vascular disease, history of keloid formation, patients currently receiving anticoagulation therapy or systemic corticosteroids, and patients known to have hypersensitivity to topical antibiotics shall be excluded from the study.

Participants may request to withdraw from the study at any time. A participant may also be withdrawn from the study if the primary investigator believes that the participant was non-compliant with the treatment guidelines or develops severe and intolerable adverse effects (e.g. hypersensitivity reaction) secondary to the treatment given.

C. Randomization and Blinding

Randomization

Assignment of participants to the experimental (hydrocolloid dressing) or control group (topical antibiotic) will be done using the fishbowl method by a research assistant.

Blinding

Participants and the physician assessors will be blinded with the treatment assigned.

D. Baseline Data Collection

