On the first visit, informed consent will be obtained from the patient. Afterwards, the following data will be recorded by the primary investigator on the baseline general information sheet: study code assigned to each individual patient, age, sex, and anatomic sites involved.

Photographs will be limited to the skin punch biopsy sites and will be taken at baseline using a DSLR camera with uniform distance (3 inches) and lighting.

On the 5th day after the skin punch biopsy procedure, the following data will be recorded by the physician assessors: the presence or absence of infection, the clinical estimate of reepithelialization, the clinical estimate of wound closure, scar formation, pigmentation of scar, and the cosmetic appearance of the wound. The primary investigator will then collect the wound evaluation sheets from the physician assessors. Photographs of the biopsy site will also be taken.

E. Intervention

Before the biopsies will be performed, the sites will be cleansed with 70% isopropyl alcohol and anesthetized intradermally with 1% lidocaine hydrochloride.

No suture, electrocautery, aluminum chloride or other hemostatic agents will be applied to the biopsy sites to avoid inhibition of wound healing inherent with these agents.

Once bleeding will be controlled by pressure, wounds will be dressed with either a 1-inch size Duoderm Control Gel Formula hydrocolloid dressing or gauze dressing impregnated with mupirocin ointment covered by a transparent dressing (Tegaderm). Dressings will be left in place for 5 days, after which the dressings will be removed and will be cleansed with water to remove any exudate.

F. Assessment

For this study, wound assessment will be done after 5 days. Dermoscopy and photographs of the wounds will be taken for every evaluation.

According to a study entitled “Pathophysiology of Acute Wound Healing” by [name] et. al. published in Elsevier Clinics in Dermatology in 2007, there are three phases of wound repair that overlap in time. These are the inflammatory reaction phase, proliferation phase, and remodeling phase. Days after initial injury, the wound would be in the proliferative phase where there would be reepithelialization of the wound, the establishment of appropriate blood supply, and reinforcement of the injured dermal tissue.^[14]

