Three physician assessors who will be trained in the evaluation of skin punch biopsy wounds and the scoring criteria that will be used in this study will assess the wound and record their evaluations individually.

SAMPLE SIZE AND STATISTICAL ANALYSIS

Using G*Power 3.1.9.7, a minimum of 56 patients or 28 per group are required for this study based on the 8.38 mean Scar appearance score on Hydrocolloid

dressing versus 7.23 mean Scar appearance score on Conventional daily dressing.^[15] This computation also accounts for desired 1.5 common standard deviation, 5% level of significance and 80% power.

Descriptive statistics will be used to summarize the demographic and clinical characteristics of the patients. Frequency and proportion will be used for categorical variables and mean and SD for normally distributed continuous variables. Independent Sample T-test and Fisher's Exact/Chi-square test will be used to determine the difference of mean and frequency, respectively, between patients undergoing Hydrocolloid Dressing versus Topical Antibiotic. All statistical tests will be two tailed tests. Shapiro-Wilk test will be used to test the normality of the continuous variables. Missing values will neither be replaced nor estimated. Null hypotheses will be rejected at 0.05 α -level of significance. STATA 13.1 will be used for data analysis.

Inter-rater and Intra-rater reliability will also be conducted.

SAFETY EVALUATION

Assessment of possible adverse effects due to the hydrocolloid dressing or the topical antibiotics will be done on follow-up visit. Complaints of pruritus, burning, or stinging sensation will be asked from participants, while other physical signs and symptoms of adverse effects to the treatment applied will be checked by the primary investigator.

ETHICAL CONSIDERATIONS

This study will be conducted in accordance with the accepted ethical research practices of the ICH Good Clinical Practice regulations and guidelines. The study will

be explained thoroughly to the eligible patients prior to enrollment. Free and informed written consent will be obtained.

INFORMED CONSENT

All participants involved in the study will not be compromised in terms of treatment. All possible benefits and side effects of the treatment will be fully explained and must be understood by the patients prior to enrollment into the study.

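### Patients can be withdrawn from the study after randomization, and the readable text does not require them to be scored on day 5 or kept in the analysis; the likely effect is small and the remedy cheap

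*Combined protocol and SAP*

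**What the plan says.** Section B (Patient Selection, Recruitment and Withdrawal) gives two investigator-led grounds for leaving the study. The first is "A participant may also be withdrawn from the study if the primary investigator believes that the participant was non-compliant with the treatment guidelines". The second is that the patient "develops severe and intolerable adverse effects (e.g. hypersensitivity reaction) secondary to the treatment given". Patients may also leave at their own request.

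Section E (Intervention) says "Dressings will be left in place for 5 days, after which the dressings will be removed". Section F adds "For this study, wound assessment will be done after 5 days", and no other scoring time is described. On absent data, the statistical section says only "Missing values will neither be replaced nor estimated". It names no analysis set.

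Under Expected Outcomes in the Project Summary, "The primary outcome measure is the proportion of patients who achieved better overall healing when treated with hydrocolloid dressing". Under Safety Evaluation, "Assessment of possible adverse effects due to the hydrocolloid dressing or the topical antibiotics will be done on follow-up visit", and day 5 is the only such visit described. The Risks section separately says that treatment stops for any adverse side effect, and is silent on whether the wound is then scored.

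**The concern.** Randomization makes the two arms comparable only if the patients analysed are those who were randomized. Section B allows some to leave afterwards, on grounds that can be related to the result. The adverse-effect ground is tied by its wording to the assigned treatment. The non-compliance ground rests on the investigator's belief, and a dressing that comes off early may do so more often in one arm or on a worse wound.

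With one scoring occasion there is no earlier score to fall back on. A patient withdrawn before day 5 contributes nothing, and the no-replacement rule leaves it so. Because the primary outcome is a proportion of patients, who remains in the denominator is part of the endpoint. If losses differ by arm and relate to healing, the estimate shifts in a direction the documents do not fix.

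**Working it through.** **Reproducing the plan's figure.** Inputs from the statistical section: means 8.38 and 7.23, SD 1.5, two-sided 5% level, 80% power. The standardized difference is (8.38 − 7.23)/1.5 = 0.767. The noncentral t gives power 0.789 with 27 per arm and 0.804 with 28. The stated 28 per group (56 in total) is therefore reproduced, as a number with no allowance for withdrawals.

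**Tracing a withdrawn patient.**
1. Withdrawn at an unscheduled contact before day 5: no score exists, nothing in the readable text requires one to be obtained, and none is imputed. The patient drops out.
2. Withdrawn at or after the day-5 visit: scores may already exist. The text neither orders them discarded nor says they are kept.
3. Treatment stopped under Risks without withdrawal under section B: the general day-5 schedule applies, but scoring after stopping is not addressed.

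**Size for the four-category scales.** The documents give no withdrawal rate or category probabilities, so these are assumptions. There is no true effect, each arm has 28 patients, one arm loses k = 1 to 4 and the other loses none. The test is Pearson chi-square at 5%, with 200,000 simulated trials per case. Four distributions were used, in percent from worst to best category. Cells give type I error (%) for k = 1, 2, 3, 4.

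| Distribution | No loss | Lost at random from the worse 14 | Exactly the k worst lost |
|---|---|---|---|
| 25/25/25/25 | 5.0 | 5.0, 5.2, 5.5, 6.2 | 5.9, 8.0, 11.7, 17.4 |
| 5/15/30/50 | 4.2 | 4.2, 4.2, 4.4, 5.0 | 5.3, 7.3, 10.5, 14.7 |
| 10/30/40/20 | 4.7 | 4.6, 4.7, 4.9, 5.4 | 6.0, 8.2, 10.4, 12.6 |
| 40/30/20/10 | 4.6 | 4.6, 4.8, 5.2, 6.0 | 5.0, 5.9, 7.5, 10.2 |

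A rerun agreed to within about 0.1 percentage points. In the worse-half column the largest rise over no loss is 6.0 − 4.6 = 1.4 points, at four losses. With one or two losses it is at most 0.2 points.

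**Infection.** For Fisher's test by exact enumeration, removing up to k infected patients from one arm gives 1.7, 3.0, 4.0 and 4.8% when 10% are infected (0.8% with no loss). It gives at most 0.25% at 5% infected and 0.0% at 2% infected. It stays below 5% throughout.

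**Denominator.** Start from an assumed 14/28 = 50.0%. If those lost are all non-successes, the proportion becomes 14/27 = 51.9% with one lost and 14/24 = 58.3% with four. If all are successes, it becomes 13/27 = 48.1% and 10/24 = 41.7%. Losses wholly at random give no bias.

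**The case against.** The strongest reply is that permission is not exclusion. Section B says a patient may be withdrawn. Nothing orders recorded scores to be deleted, and a rule against replacing missing values concerns scores that do not exist. Opportunity is limited too: one dressing stays on for five days, adverse effects are checked at the visit where scores are due, and patients with poor healing tendency or known antibiotic hypersensitivity are excluded beforehand. The illustrations put every loss in one arm; similar losses in both would partly cancel. The 14/28 example is arithmetic only, since the plan does not define better overall healing for an individual patient. Figure 1 is not shown and might include a follow-up or analysis box.

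All of this stands as a limit on weight. It does not remove the route by which a patient withdrawn before scoring is lost, on grounds that can depend on the dressing or the wound.

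A reader might go further and infer that the plan deletes withdrawn patients' data; it does not say so. A reader might also infer that an unblinded investigator will choose whom to remove. The blinding statement, "Participants and the physician assessors will be blinded with the treatment assigned", omits the investigator, but nothing says the investigator knows the arm, and the concern does not depend on it. Finally, the 17.4% might be taken as the expected error rate. It requires four losses, all in one arm, that are exactly its four worst wounds.

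**Conclusion.** The concern holds in a limited form. Section B allows withdrawal from the study after randomization, on grounds that can be related to treatment or wound, and the readable text does not secure day-5 scoring or retention of those patients. Followed as written, it permits selective loss; it does not show that any will occur.

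The size cannot be derived from the documents and is probably small: type I error of about 4% to 6% on the four-category scales under moderately selective loss of 1 to 4 of 28 patients from one arm. The roughly 17% figure is an extreme upper bound. All these figures rest on assumed loss rates, assumed category distributions and no loss in the other arm. No crossover is described, so the main question is who is scored and kept, not which arm they count in. This is a worthwhile, inexpensive improvement and not a fatal flaw. Confidence is medium.

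**What to change.** Amend section B so that non-compliance, or stopping or losing the dressing, does not by itself end study participation. State in the assessment and statistical sections that:

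- every randomized patient who has not withdrawn consent is scored at the day-5 visit;
- scores already recorded are kept;
- all are analysed in the assigned arm;
- withdrawals are reported by arm with reasons.

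Reconcile section B (withdrawal from the study for severe and intolerable effects) with Risks (stopping treatment for any adverse side effect) so that both say what happens to day-5 scoring. No position is taken here on when a dressing should be stopped.

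The cost is wording, since the day-5 visit is already planned and the sample size does not change. The downside is that the estimate will include non-adherent patients and may be slightly smaller.

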The primary investigator will explain the study objectives, procedure, risks, and benefits to the eligible patients. Patients will be encouraged to ask questions regarding the study. In order to affirm voluntary participation, the patients will be asked to sign a written informed consent form (ICF) available in both English and Filipino versions (attached separately). One copy of the ICF will be given to the patient for reference. Another consent taker will be provided if the participant is a patient of the primary investigator.

CONFLICT OF INTEREST

This study is investigator-initiated and not industry funded or company sponsored. There is no potential conflict of interest.

PRIVACY AND CONFIDENTIALITY

All data will be handled in compliance to the Data Privacy Act of 2012 and its implementing rules and regulations in 2016.

The identity, personal data, and other medical information of patients will remain confidential. In the event of any publication regarding the study, the identity of the patients will remain confidential.

Physical data will be securely filed and electronic data will be stored in an encrypted hard drive by the principal investigator. Both forms of data will be protected from illegal or inadvertent access. Only the primary investigators, study coordinators, and the statistician will have access to the information collected for this study.

Physical data will be shredded and securely disposed of one year after the completion of this study. Electronic data will be stored for a maximum of three years after completion of this study after which all data will be permanently deleted.

The records, to the extent of the applicable laws and regulations, will not be made publicly available. However, the UST Hospital – Research Ethics Committee (USTH-REC) will be granted direct access to the participant's original medical records to check study procedures and data, without making any of the information public. The informed consent form that patients will sign prior to participation in the study will include a section that they are authorizing such access to the study and medical records.

VULNERABILITY

Patients aged 18 years old to 64 years old with clean cutaneous lesions who will undergo skin punch biopsy will be recruited in this study. No patients aged below 18 years old or above 64 years old, prisoners, mentally handicapped, or those with incurable diseases will be included.

RISKS

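### The plan claims double-blinding with participants blinded, but patients wear one of two visibly different dressings and no concealment is described; as described, the trial is at most assessor-blinded

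*Combined protocol and SAP*

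**What the plan says.** The design label appears in the title, again on the title line of the summary page, in the Project Summary (Methodology and Population: "The study is a double-blind randomized controlled trial which will be conducted at the Dermatology outpatient department"), in the protocol title under General Information, and in Methodology A, Study Design ("This is a double blind randomized controlled trial that will be conducted at the outpatient department"). Methodology C, Randomization and Blinding, says who is blinded: "Participants and the physician assessors will be blinded with the treatment assigned". It gives no method.

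Methodology E, Intervention, describes the two arms, the cover being a transparent film: "wounds will be dressed with either a 1-inch size Duoderm Control Gel Formula hydrocolloid dressing or gauze dressing impregnated with mupirocin ointment covered by". It continues: "Dressings will be left in place for 5 days, after which the dressings will be removed and will be cleansed with water".

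Under Informed Consent: "The primary investigator will explain the study objectives, procedure, risks, and benefits to the eligible patients". The Main Objective names both dressings.

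On who rates the outcomes, Methodology D lists six items, cosmetic appearance among them, and says: "On the 5th day after the skin punch biopsy procedure, the following data will be recorded by the physician assessors". Methodology F has three trained physicians who "will assess the wound and record their evaluations individually". Item 6 of the Scoring Criteria, however, glosses cosmetic appearance as the patient's acceptance. The Safety Evaluation has participants asked about pruritus, burning and stinging. The statistical section plans inter-rater and intra-rater reliability without saying which items it covers.

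**The concern.** A hydrocolloid patch and a gauze with ointment differ in kind, and a transparent film hides neither. A patient who can see the biopsy site can see what is on it for the whole 5 days. The claim is that participants do not know the treatment assigned, and here the treatment assigned is the dressing itself.

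At stake is what a reader may conclude from anything the patient reports. Under a double-blind label, reported symptoms would be credited with protection from expectation that the described procedures do not give. The same holds for cosmetic appearance if that is the patient's judgement: a difference between arms could then reflect opinion of the dressing rather than healing.

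**Working it through.** No arithmetic decides this point, so the relevant sections are set side by side.

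1. **Participant blinding.** Section C claims it. Section E describes two physically different dressings worn for 5 days. The wording of section E leaves open whether the transparent film goes over both dressings or only the gauze, but a transparent cover would not conceal the difference either way. No opaque cover, sham or matched appearance is mentioned in the readable text. Some sites may be out of the patient's view, but section B does not limit enrolment to such sites.

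2. **What patients are told.** The consent discussion covers the objectives and the procedure, and the objective names both dressings. It is therefore plausible that patients could recognise which one they have. The consent text is not available, so this is an inference.

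3. **Assessor blinding.** Section C states it. It is feasible, because section E has the dressing removed and the site cleansed, and this can come before assessment. The readable text does not say who does this or whether the assessors are absent.

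4. **Cosmetic appearance.** Three readings fit the text:
   - the physicians give their own judgement (sections D and F);
   - the patient gives the rating (Scoring Criteria, item 6);
   - the physicians write down the patient's answer, which would satisfy both passages.

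   Under the second and third readings the item is a patient-reported outcome without described blinding. Inter-rater reliability would then have no independent second rater for it, because three physicians recording one patient's answer are not three judgements.

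5. **Symptoms.** Pruritus, burning and stinging come from the participant whichever reading of item 6 is right.

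6. **Places to change.** Title 1 + title line of the summary page 1 + Methodology and Population 1 + protocol title under General Information 1 + Study Design 1 = 5 uses of the label. Adding the sentence in section C gives 5 + 1 = 6.

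7. **Sample size.** The plan's own figure does not depend on blinding, and it reproduces. The difference is 8.38 − 7.23 = 1.15, and 1.15 / 1.5 = 0.767 standard deviations. A two-sided 5% t-test with 80% power needs 27.70 per group, rounded up to 28, or 56 in all. Power at 28 per group is 80.4%. Nothing in this point alters it.

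**The case against.** The strongest reply is that the documents show only that no method of blinding participants is described, which is less than showing that every participant is unblinded. Figure 1 and the consent form are unseen, a wound on the back may never be seen by its owner, and a patient may see a dressing without knowing which one is experimental. The first two of these stand as limits. The third does not rescue the claim, because section C says participants are blinded to the treatment assigned, not merely to which arm is of interest.

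Second, the plan need not contradict itself on cosmetic appearance. Recording is compatible with writing down the patient's answer, and patient acceptance could be a physician's view of acceptability. This stands: the passages are ambiguous, and a contradiction is not established.

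Third, the practical reach is limited. Five of the six efficacy items are physician assessments declared blinded, and the dummy tables plan no comparison of symptoms between arms. Table 2 already sets cosmetic appearance in its own block, and no pooling of patient and physician ratings is stated. This also stands, and it limits the consequence without supporting the label.

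A reader might go further and infer that the assessors are unblinded too, or that the efficacy results will be biased. The documents support neither. Assessor blinding is stated and can be achieved; leaving out who removes the dressing is a matter of operating detail, which Figure 1 may cover. The documents give no figure from which a bias could be sized.

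**Conclusion.** The point holds, with high confidence for its main part. The plan claims blinding of participants, and its described procedures do not provide it. As described, the trial is at most assessor-blinded. This rests on the readable text and would fall if Figure 1 or the consent form set out a workable way of concealing the dressing.

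The question of whose judgement item 6 records is an ambiguity to clear up, held with moderate confidence. Securing assessor blinding in practice is a suggestion only.

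The countable size is six places in the protocol. No bias or false-positive rate is claimed. The effect on the primary outcome cannot be determined, because better overall healing is not defined and the plan does not say whether cosmetic appearance enters it. The trial remains viable; this should be fixed before results are reported under the present label.

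**What to change.** - **Label.** Replace double-blind with assessor-blinded at its five uses, and reword the sentence in section C to claim blinding of the assessors only. The alternative is to describe a workable method of concealing the dressing from patients and keep the label.
- **Symptoms.** When pruritus, burning and stinging are reported, state that they are not protected by blinding.
- **Cosmetic appearance.** Reconcile sections D and F with item 6 of the Scoring Criteria by stating whose judgement it is; that choice is the investigators'. If it is the patient's, given directly or written down by a physician, report it as an unblinded patient-reported outcome and leave it out of the inter-rater reliability analysis.
- **Suggestion.** Have an existing staff member who is not an assessor remove the dressing and cleanse the site before the assessors see the wound.

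The cost is six wording changes, one clarifying sentence on item 6 and a line on reporting symptoms. The suggestion, if taken up, adds a small change to the day-5 workflow. The trial loses the double-blind label, and the ethics and consent papers (English and Filipino) may need amending. The number of patients and the visits are unchanged.
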